Study Design and Location(s)

This study will be conducted as a double-blinded, placebo-controlled randomized clinical trial.

We propose two arms to test BSS against placebo:

1. BSS 4 tablets po bid (2.1 grams total of BSS)
2. Placebo 4 tablets po bid

Study participants will be recruited from The New York Center for Travel and Tropical Medicine Clinic in New York, New York, USA (see Procedures) (<http://www.travelhealth.net/>). Throughout the study period, the recruiting site will maintain adequate personnel trained in the study protocol and procedures (see Training for Study Personnel). Study personnel will be available to communicate with the co-PIs as necessary and to address issues with the study protocol and concerns of the study participants. This site will be able to consent and enroll participants (see Procedures for Implementing and Documenting Informed Consent), store and distribute the study drug and placebo, and collect and safely store questionnaire data (see Data Handling and Analysis) and biologic samples (stool) data (see Biologic [stool] Specimen Collection and Testing), in accordance with the study protocol.

Objectives

1. (Hereafter, “primary objective”) Test the efficacy of BSS in the prevention of TD among international travelers.
2. (Hereafter, “secondary objective”) Determine the impact BSS has in the acquisition of gut AMR genes among international travelers.

Hypotheses

The following hypotheses follow the objectives above:

1. NULL HYPOTHESIS: BSS does not prevent TD among international travelers.
 - a. Does BSS prevent TD among international travelers?
 - b. Does BSS reduce severity/frequency of TD among international travelers?
2. NULL HYPOTHESIS: BSS does not alter the acquisition of gut AMR genes among international travelers.
 - a. Does BSS affect the acquisition of gut AMR genes among international travelers?

- b. Does BSS affect the acquisition of gut AMR genes among international travelers that develop TD?
 - i. Does BSS alter the acquisition of gut AMR genes if an international traveler with TD takes an antimicrobial while taking BSS?
- c. Does BSS affect the acquisition of gut AMR genes among international travelers that do not develop TD?

General Approach

The approach of this study will be hypothesis-testing.

Procedures and Methods

Design

Statement of Purpose

The purpose of this study is to investigate the impact of BSS on the acquisition of TD and acquisition of gut AMR genes among international travelers.

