Includes the 7 days prior to departure in which the pre-travel questionnaire and a biologic (stool) specimen is collected, the full duration of travel, and through 10 days maximum post-return from travel, or until both the post-travel questionnaire and submission of the post-travel biologic (stool) specimen is complete (a maximum of 17 days post-travel)

Travel companion (group):

Two or more study participants with a common relation (friends, colleagues, or relatives) with the same itinerary, who anticipate performing the same activities during travel

Trip duration:

The number of days spent in country; excludes air travel time

Severe TD:

Hospitalization to an inpatient ward either during travel or after travel with a diagnosis of diarrhea

Acquisition of AMR gene(s):

The presence in a post-travel biologic (stool) specimen of one or more antimicrobial resistance gene(s) that were not present in a pre-travel biologic (stool) specimen from the same person, and which is known to confer antimicrobial resistance to one or more antimicrobial agents ("resistome")

Medication compliance:

Full = participant takes all scheduled doses according to directions

Good = If <15% of BSS or placebo doses were missed during travel

Fair = If 15–30% of BSS or placebo doses were missed during travel

Poor = If >30% of doses were missed during travel

Questionnaire compliance:

Full = participant completes all questionnaires

Good = participant completes >80% of all during travel questionnaires, AND
both the pre- and post-travel questionnaires

Fair = participant completes between 30–80% of all during travel
questionnaires, including AT LEAST the pre-travel questionnaire

Poor = participant completes <40% of all during travel questionnaires, and AT
LEAST the pre-travel questionnaire

Biologic (stool) specimen compliance:

Full = BOTH specimens collected and sent

Fair = ONLY one specimen collected and sent

Poor = No specimens collected and sent

Loss to follow-up:

Failure to complete the post-travel questionnaire after three attempts to contact the participant or if submission of the post-travel biologic specimen (stool) occurs more than 10 days after return from travel or is not submitted

Participant Inclusion Criteria

Willing participants must meet the inclusion criteria as outlined here:

1. Be ≥ 18 and <70 years of age at the time of enrollment

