Participants will be provided two OMNIgene gut kits at their pre-travel consultation/enrollment visit once enrolled (see Biologic [Stool] Specimen Data Collection and Testing). These kits will come with instructions on use, handling, and shipment.

In the event that participants are able to provide a stool sample while in clinic for their pre-travel consultation/enrollment visit or during a non-study post-travel follow-up sick visit within 10 days of return, these samples will be aliquoted by study personnel at The New York Center for Travel and Tropical Medicine in the following manner:

*First, the required quantity will be placed in the participant's OMNIgene gut kit (per manufacturer directions) to be sent to CDC's Clinical and Environmental Microbiology Branch for resistome testing. The remainder will be frozen, and sent to CDC for analysis at a later date (note: OMNIgene gut kit does not allow for culture - a see Biologic [Stool] Specimen Collection and Testing). Only those participants who happen to have a biologic (stool) specimen collection completed at the clinic will have their stool analyzed by culture; this is not a requirement for participation and no additional compensation above that previously described will be offered.

Table 3. Schedule of LABORATORY events (secondary objective)

(Events from Table 2 still apply to these participants)

	Stages		
	Pre-travel	During travel	Post-travel
Biologic (stool) sample	X		X
Laboratory testing of stool	X		X

Analytic tests

Questionnaires: Data from the questionnaires will be analyzed for statistical significance comparing intervention vs placebo groups.

Biologic (stool) specimens: A highly multiplexed PCR assay detecting over 500 different AMR genes will be used to test the DNA extracted from all biologic (stool) specimens that were placed in the OMNIgene gut kit (see Biologic (Stool) Specimen Collection and Testing). Results will be analyzed to determine if the participants acquire gut AMR genes (changes to the “resistome”) as a result of travel and whether or not that change varied with the bismuth subsalicylate treatment received. Additionally, stool bacteriologic culture will be performed on those specimens submitted in clinic.

Intervention

We propose the inclusion of two arms to test BSS against placebo:

1. BSS 4 tablets po bid (2.1 grams total)
2. Placebo 4 tablets po bid

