Dosing will begin on the flight prior to arrival in the destination and will cease once they return home. The study medications must be taken twice daily (a morning and an evening dose); with time zone changes, the first dose should be taken to ensure that no longer than 12 hours passes before a subsequent dose.

Before departure, participants will be provided, free of charge, all needed study medication for the duration of their trip. Participants will be encouraged to take all doses of their medication and appropriately document on their daily during travel questionnaires if a dose was missed or taken off schedule.

Outcomes

The outcomes of this study will include:

	Favorable Outcome	Non-favorable Outcome
Hypothesis 1: Prevention of TD	Prevention of TD in the intervention group	TD in the intervention group at a rate similar to placebo; intervention drug side effects; adverse events

Hypothesis 2: Acquisition of AMR genes	Reduced or no presence of travel-associated gut AMR genes in the intervention group	No reduction in the presence of travel-associated gut AMR genes in the intervention group
---	---	---

The participant's study period will end in the following circumstances:

1. The traveler meets criteria for removal (see Criteria for Removal from the Study)
2. The participant voluntarily withdraws from the study (see Procedures for Implementing and Documenting Informed Consent)
3. The participant completes all study activities and submits all study questionnaires and biologic (stool) specimens
4. The participant is lost to follow-up

The participants will be instructed at enrollment to stop the study medication for any of the following reasons (although they will still be instructed to answer their questionnaires and submit biologic [stool] specimens as scheduled):

1. Antibiotics or BSS (either provided by the study personnel for TD treatment, or taken as an over-the-counter remedy) are taken for TD or for another medical condition
2. Any severe adverse events as described, such as signs and symptoms of salicylism or neurotoxicity, occur
3. Hospitalization for any reason

Barring the reasons listed above, the study medication should be taken throughout the trip duration, even if diarrhea occurs, if possible.

Criteria for Removal from the Study

Participants will be removed from the study when any of the following criteria apply:

1. Do not complete the pre-travel questionnaire (see Definitions for compliance)
2. Loss to follow-up (see Definitions)

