APPENDIX I: Data Analysis Table Shells

Table 1. Baseline Characteristics of Participants

	BSS	Placebo	P-value
Demographics			
Age			
Sex			
Race			
Ethnicity			
Medical History			
Chronic medical conditions			
Tinnitus			
Antibiotics between 30 to 90 days prior to travel			
Probiotics within 30 days			
Travel			
Duration of travel			
Primary reason for travel			
Secondary reasons for travel			
Attended provider (by type)			

Table 2. Odds ratios (OR) of TD associated with BSS among international travelers, adjusting for select factors

	Total, N	TD, %	OR (95% CI)
Tablets			
BSS			
Placebo			Ref
Age groups, years			
≥18			
Sex			
Male			
Female			Ref
Race/ethnicity			
Travel region			
Travel duration			

Table 3. The proportion of participants having resistance genes before and after travel; acquiring, losing, or maintaining genes after travel

	All participants	BSS	Placebo	P-value
Pre-travel				
Gene 1				
Gene 2				
Gene 3				
Gene 4				
...				
Post-travel				
Gene 1				
Gene 2				
Gene 3				
Gene 4				
...				
Acquisition of gene				
Gene 1				
Gene 2				
Gene 3				
Gene 4				
...				
Loss of gene				
Gene 1				
Gene 2				
Gene 3				
Gene 4				
...				
Maintenance of gene				
Gene 1				
Gene 2				
Gene 3				
Gene 4				
...				

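### Table 3 gives the resistance-gene objective only per-gene arm proportions and a P-value: no interval or N for the BSS–placebo contrast, and no row for the defined participant-level outcome

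*Combined protocol and SAP*

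**What the plan says.** The secondary objective (Objectives, item 2) is to "Determine the impact BSS has in the acquisition of gut AMR genes among international travelers". The Definitions section makes acquisition a participant-level event: "The presence in a post-travel biologic (stool) specimen of one or more antimicrobial resistance gene(s) that were not present" in the same person's pre-travel specimen.

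Under Analytic tests, the assay is "A highly multiplexed PCR assay detecting over 500 different AMR genes". The results are to show whether participants acquire genes "as a result of travel and whether or not that change varied with the bismuth subsalicylate treatment received". No effect measure, interval or model is named there.

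The Outcomes table lists as the non-favorable result for hypothesis 2: "No reduction in the presence of travel-associated gut AMR genes in the intervention group".

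Appendix I holds the analysis shells:

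- **Table 2 (TD)**, "Odds ratios (OR) of TD associated with BSS among international travelers, adjusting for select factors", has columns for total N, TD percentage and odds ratio with 95% CI.
- **Table 3 (AMR)**, "The proportion of participants having resistance genes before and after travel; acquiring, losing, or maintaining genes after travel", has columns for all participants, BSS, placebo and P-value. Its blocks are pre-travel, post-travel, acquisition, loss and maintenance, and every row in every block is a single gene.

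The Sample Size and Power Calculation section sizes the trial on TD alone.

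**The concern.** The objective asks how large an effect BSS has on acquisition. The only inferential output planned for that question is a P-value per gene. A P-value mixes the size of a difference with the precision of its estimate. When it is above 0.05, a reader needs an interval to see whether a useful reduction has been ruled out or merely not demonstrated. Table 3 prints no interval, and it has no N from which to build one.

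The shell also omits the outcome that the protocol defines. Acquisition of at least one new gene by a participant is a single yes/no result per person, and would give one interpretable contrast between arms. Table 3 replaces it with more than 500 separate gene rows.

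Current State of Knowledge describes the effect of BSS on AMR acquisition as unknown, so this is the new question of the trial. It receives a weaker report than TD does in the same appendix.

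**Working it through.** **1. Is the estimate supplied elsewhere?** The places where it could appear, in the available text:

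| Place | Effect measure for AMR | Interval | Participant-level acquisition |
|---|---|---|---|
| Definitions | none | none | defined |
| Analytic tests | none | none | not carried into an estimate |
| Outcomes table | reduction or no reduction | none | not specified |
| Appendix I, Table 3 | arm proportions per gene | none | no row |

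**2. The plan's own figure.** The stated size is 244 per arm for TD at 40% versus 28%, alpha 0.05, power 80%. With mean rate 0.34:

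n = [1.96·√(2·0.34·0.66) + 0.8416·√(0.40·0.60 + 0.28·0.72)]² / 0.12² = (1.313 + 0.559)² / 0.0144 = 243.4, rounded up to 244.

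The figure reproduces (two-sided, pooled variance, no continuity correction). No such figure exists for AMR.

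**3. Inputs for the illustration.** The documents give no acquisition rate, so 10% to 60% on placebo is assumed. Two sizes are shown:

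- 244 per arm, from the sample size section.
- 125 per arm, from Table 5 of the budget, which costs diagnostic testing for 250 participants (equal split assumed). Analytic tests says that all kit specimens are tested, so 125 may be too low.

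Participants are treated as independent.

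**4. What an interval adds.** With p₁ for BSS and p₀ for placebo:

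- Risk difference (RD): p₁ − p₀ ± 1.96·√[p₁(1−p₁)/n + p₀(1−p₀)/n]
- Risk ratio (RR): (p₁/p₀)·exp{±1.96·√[(1−p₁)/(n·p₁) + (1−p₀)/(n·p₀)]}
- P: two-sided z-test with pooled variance

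Placebo 50/125 versus BSS 38/125 (40.0% versus 30.4%):

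- z = 0.096/√(2·0.352·0.648/125) = 0.096/0.0604 = 1.59, P = 0.11
- RD = −9.6 points (−21.4 to +2.2)
- RR = 0.76; log standard error √(1/50 − 1/125 + 1/38 − 1/125) = 0.174; 95% CI 0.54 to 1.07

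Placebo 98/244 versus BSS 79/244 (40.2% versus 32.4%):

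- P = 0.07
- RR = 0.81 (0.64 to 1.02)

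No observed difference, 30% in both arms:

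- 125 per arm: RD ±1.96·√(2·0.3·0.7/125) = ±11.4 points; RR 0.68 to 1.46
- 244 per arm: RD ±8.1 points; RR 0.76 to 1.31

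At 125 per arm, even identical observed rates would not exclude a 30% relative reduction, since the lower limit of 0.68 lies below 0.70. At 244 per arm they would exclude it (lower limit 0.76). The P-value is 1 in both cases and does not show this.

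**5. How likely is a non-significant result if BSS works?** Power for a true 30% relative reduction, two-sided 0.05:

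| Placebo rate | 125 per arm | 244 per arm |
|---|---|---|
| 10% | 13% | 22% |
| 20% | 24% | 42% |
| 40% | 52% | 80% |
| 60% | 82% | 98% |

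For genes acquired by 20% or fewer, non-significance is the more likely result at either size.

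**The case against.** Three stronger readings are tempting, and the documents support none of them.

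- **That Table 3 gives no effect size, so a real reduction and a null would look alike.** They would not. The arm proportions are printed: 40% versus 30.4% with P = 0.11 is visibly different from 30% versus 30% with P = 1. The crude difference and ratio follow by subtraction and division. What is missing is their precision.
- **That the within-person travel question cannot be answered.** The acquisition and loss blocks are the discordant cells of the paired comparison. If both use participants with two stools as the denominator, acquired minus lost is one subtraction. Again only the interval is absent.
- **That the protocol will declare no reduction whenever P exceeds 0.05.** The Outcomes table states no decision rule. A reader might infer one, because P is the only inferential output in the shell, but it is not written.

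It is also fair to say that the 40% illustration is not a per-gene rate from the documents, and that ratios for over 500 genes would meet zero cells and raise multiplicity. At 0.05 per gene, 500·0.05 = 25 false positives per block would be expected if every null were true. Finally, this is a shell for a secondary objective, and an interval could be added at analysis from the same data.

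These points narrow the concern and shape the fix. They do not remove it: the plan as written contains neither an interval nor a row for its own defined outcome.

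**Conclusion.** The point holds in this form: Table 3 reports AMR gene by gene as arm proportions with a P-value, without interval or N for the BSS–placebo contrast and without the participant-level acquisition outcome, while TD gets an odds ratio with a 95% CI. The absence is a matter of reading the text and rests on no assumption.

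The size of the consequence does rest on assumptions: a placebo acquisition rate of 10% to 60%, and 125 or 244 evaluable participants per arm. Within that range, power for a 30% relative reduction runs from 13% to 98%. The interval therefore matters most for rarer genes or if only the costed 250 participants are tested, and least for a common outcome in the full sample.

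Severity is minor to moderate. Sample size, data collection and conduct are unaffected.

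**What to change.** In Table 3, before the treatment code is broken:

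1. Add a first row for participant-level acquisition (at least one new gene, among participants with both stools), with n/N per arm and the BSS-minus-placebo risk difference and risk ratio, each with a 95% CI. State that the AMR conclusion will be drawn from this interval.
2. In the per-gene rows, add n/N and a risk difference with a 95% CI by a method that remains valid with zero cells, such as a Newcombe or Miettinen–Nurminen score interval. Label these rows exploratory.
3. Optionally, for the travel question, add acquired minus lost with a 95% CI for paired proportions, overall and by arm.

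The cost is a shell edit and some extra SAS code on data already collected. The table becomes longer: an interval for each of 500 genes in four blocks (post-travel, acquisition, loss, maintenance) is about 2,000 intervals, and many will be visibly wide. Multiplicity across genes is a separate issue that this change does not settle.
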